5 STUDY ACTIVITIES

5.1 Eligibility Criteria

Subjects must meet all of the following criteria in order to be included in the study. Anything other than a positive response to the questions below will result in exclusion from study participation.

Consent

1. Subjects or their legally authorized representative (if permitted per local regulations) must voluntarily sign and date an informed consent (and assent for minors as required by applicable regulation), approved by an independent ethics committee (IEC)/institutional review board (IRB), prior to the initiation of any screening or study-specific procedures.

Demographic and Laboratory Assessments

- 2. Adult or adolescent, age 12 years and older.
- 3. Subject must be able to understand and adhere to the study protocol and study visit schedule in the opinion of the investigator.
- 4. Subject must not have any of the following abnormal laboratory results at screening:
 - Albumin < 2.8 mg/dL for subjects with cirrhosis, < lower limit of normal for subjects without cirrhosis;
 - International normalized ratio (INR) > 1.5 × ULN, unless subject has known hemophilia or is on a stable anticoagulant regimen affecting INR;
 - Hemoglobin < 10 g/dL;
 - Platelets < 50,000 cells per mm³ for adult subjects with cirrhosis; < 90,000 cells per mm³ for adult subjects without cirrhosis; < 40,000 cells per mm³ for subjects aged < 18 years regardless of cirrhosis status;
 - Calculated creatinine clearance < 30 mL/min.

Subjects who have exclusionary laboratory parameters for hemoglobin and/or calculated creatinine clearance are allowed to retest 1 time within the Screening period and must meet all other eligibility laboratory criteria on the panel that is repeated. If the retest result(s) are also exclusionary, the subject may not be rescreened or retested again.

Disease/Condition Activity

- 5. Subject must have evidence of acute HCV infection prior to enrollment. Evidence of acute HCV infection is defined as physician diagnosis of acute HCV infection, quantifiable HCV RNA at Screening, and at least 1 of the following:
 - Negative anti-HCV antibody, HCV RNA and/or HCV core antigen followed by a positive HCV RNA or HCV core antigen all within an 8-month period prior to Screening;

OR

• Negative anti-HCV antibody, HCV RNA and/or HCV core antigen followed by a positive HCV RNA or HCV core antigen all within an 11-month period prior to Screening; AND risk behavior for HCV infection within 6 months prior to positive HCV RNA or HCV core antigen;

OR

 Clinical signs and symptoms compatible with acute hepatitis (ALT > 5 × ULN and/or jaundice) in the absence of a history of chronic liver disease or other cause of acute hepatitis and positive HCV RNA or HCV core antigen all within an 8-month period prior to Screening; AND risk behavior for HCV infection within 6 months prior to positive HCV RNA or HCV core antigen;

OR

- Negative anti-HCV antibody with a positive HCV RNA or HCV core antigen within a 5-month period prior to Screening.
- 6. Negative test result for hepatitis B surface antigen (HBsAg).
- 7. No evidence of chronic HCV infection for this HCV infection.
- 8. No known active SARS-CoV-2 infection. All subjects should undergo viral testing to rule out SARS-CoV-2 infection at Screening. Subjects with active SARS-CoV-2 infection may only rescreen after they meet the following SARS-CoV-2 infection viral clearance criteria:
 - At least 10 days since first polymerase chain reaction (PCR) test result have passed in asymptomatic patients; or 10 days have passed since symptom onset and at least 24 hours since resolution of fever without use of antipyretics and other symptoms improvement.
- 9. Subject with HCV/human immunodeficiency virus 1 (HIV-1) co-infection must also meet the following criteria:
 - Naïve to HIV treatment:
 - Must have a cluster of differentiation 4 (CD4+) count ≥ 500 cells/mm³ (or CD4+ % ≥ 29%) at Screening;
 - Have no plan to initiate HIV-1 antiretroviral therapy (ART) treatment while participating in this study.
 - On a stable, qualifying HIV-1 ART regimen for at least 8 weeks prior to Screening:
 - Must have CD4+ count ≥ 200 cells/mm³ (or CD4+ % ≥ 14%) at Screening, and plasma HIV-1 RNA < 50 copies/mL at Screening (by the COBAS® Ampliprep/COBAS® Taqman HIV-1 Test, v 2.0).
 - The HIV-1 ART regimen must include at least 1 of the following:
 - Raltegravir orally (per os) (PO) twice a day (BID)
 - Dolutegravir PO QD or BID
 - Rilpivirine PO QD
 - Elvitegravir/cobicistat PO QD
 - Bictegravir PO QD

In addition to the above medications, subjects may take a nucleoside/nucleotide reverse transcriptase inhibitor backbone containing any of the following:

- Tenofovir disoproxil fumarate PO QD
- Tenofovir alafenamide PO QD
- Abacavir PO QD or BID
- Emtricitabine PO QD
- Lamivudine (3TC) PO QD or BID
- Alternative HIV-1 ART regimens may be permitted with Sponsor approval.

Subject History

- I0. Subject must be HCV TN, defined as no prior treatment including interferon for this HCV infection.
- 11. Subject must be documented as either having no cirrhosis or as having compensated cirrhosis. If liver diagnostic tests are indeterminate with available diagnostic methods, subject must demonstrate absence of decompensated cirrhosis by evaluating Child-Pugh score.
- 12. Absence of hepatocellular carcinoma (HCC), for subjects with cirrhosis or with indeterminate cirrhosis status, as indicated by a negative ultrasound, computed tomography (CT) scan or magnetic resonance imaging (MRI) within 3 months prior to Screening or a negative ultrasound at Screening. Subject who has a positive ultrasound result suspicious of HCC followed by a subsequent negative CT scan or MRI or biopsy result will be eligible for the study.
- 13. No history of liver decompensation.
- 14. No history of organ transplant.
- 15. No history of severe life-threatening or other significant sensitivity to any excipients of the study drug.
- 16. Subject must not have clinically significant abnormalities, other than HCV infection, based upon the results of a medical history, physical examination, vital signs, laboratory profile, and a 12-lead electrocardiogram (ECG) that make the subject an unsuitable candidate for this study in the opinion of the investigator, including, but not limited to:
 - Uncontrolled diabetes as defined by a glycated hemoglobin (HbA1c) level > 8.5%.
 - Active or suspected malignancy or history of malignancy (other than basal cell skin cancer or cervical carcinoma in situ) in the past 5 years.
 - Uncontrolled cardiac, respiratory, gastrointestinal, hematologic, neurologic, psychiatric, or other medical disease or disorder, which is unrelated to the existing HCV infection.
- I7. Subject must not have cause of liver disease other than HCV infection, including but not limited to the following:
 - Hemochromatosis;
 - Alpha-1 antitrypsin deficiency;

- Wilson's disease;
- Autoimmune hepatitis;
- Alcoholic liver disease;
- Cholestatic liver diseases such as primary biliary cholangitis and primary sclerosing cholangitis;
- Steatosis or steatohepatitis on liver biopsy considered to be the primary cause of the liver disease rather than concomitant/incidental with HCV infection.
- I8. Subject must not have uncontrolled drug use that may impair protocol compliance in the opinion of the investigator.

Contraception

- 19. Female who is not pregnant or breastfeeding, and is not considering becoming pregnant or donating eggs during the study or for approximately 30 days after the last dose of study drug.
- 20.For all females of child-bearing potential; a negative serum pregnancy test at the Screening Visit and a negative urine pregnancy test at baseline prior to the first dose of study drug.
- 21. Female subjects of childbearing potential must practice at least 1 protocol-specified method of birth control, that is effective from Study Day 1 through at least 30 days after the last dose of study drug. Female subjects of non-childbearing potential do not need to use birth control.

Concomitant Medications

- 22. Subject must not require chronic use of systemic immunosuppressants during the study, including but not limited to, corticosteroids (prednisone equivalent of > 10 mg/day for > 2 weeks), azathioprine, or monoclonal antibodies (e.g., infliximab).
- 23. Subject must not have been treated with any investigational drug within 30 days or 10 halflives of the drug (whichever is longer) prior to the first dose of study drug or is currently enrolled in another interventional clinical study or was previously enrolled in this study.

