APPENDIX D. ACTIVITY SCHEDULE

The following table shows the required activities for this study. The individual activities are described in detail in the **Operations Manual**. Allowed modifications due to COVID-19 are detailed in the Operations Manual.

Study Activities Table

Activity	Screening (Day –30 to Day –1)	Baseline (Day 1)	Week 2	Week 4	Week 8 (EOT) or Premature D/C from Treatment	PT Week 4	PT Week 12 or PT Premature D/C
Informed consent	✓						
Eligibility criteria	· ·	✓					
Medical/surgical history (update on Day 1)	· ·	· ·					
Alcohol and nicotine use	· ·						
Adverse event assessment	· ·	✓	1	✓	1	1	 Image: A second s
Prior/concomitant therapy	· ·	•	· ·	· ·	· ·	· ·	· ·
		· ·			•		· ·
Patient Reported Outcomes (EQ-5D-5L, FSS) Questions on hepatitis C risk behaviors	✓				· · · ·		
Questions on experience with opioid substitutes and non-prescribed illicit drug use		~			×		×
* EXAMS							
12-lead ECG	 Image: A second s						
Height (screening only) and weight	 ✓ 	 Image: A second s	✓	 Image: A second s	✓	✓	✓
Vital signs	×	×	✓	×	×	×	 Image: A second s
Physical examination	~	 Image: A second s			✓		✓
Child-Pugh score (cirrhotic subjects and subjects with indeterminate cirrhosis status only)	~	×			✓		
Hepatic decompensation assessment	×	√					
HCC screen by ultrasound, if cirrhotic or indeterminate cirrhosis status	~						
Second Labs			I				
SARS-CoV-2 testing (e.g., PCR)	×						
Review of signs/symptoms of SARS-CoV-2 infection at Day 1, then as suspected		×					

Activity	Screening (Day –30 to Day –1)	Baseline (Day 1)	Week 2	Week 4	Week 8 (EOT) or Premature D/C from Treatment	PT Week 4	PT Week 12 or PT Premature D/C
CENTRAL LABS							
HIV-1 RNA (only for HCV/HIV coinfected subjects)	✓	 Image: A second s	<	 Image: A second s	✓	 Image: A second s	✓
Anti-HCV antibody, HIV antibody, and HBsAg	✓						
Hematology, clinical chemistry, urinalysis, coagulation panel	✓	×	✓	×	*	×	×
Pregnancy test (for female confirmed to have child- bearing potential [S-serum; U-urine])	√(s)	√(u)		√(u)	√(u)	√(u)	√(u)
FSH (female with no menses for > 12 months)	×						
HCV genotype/subtype	×						
Hepatitis B Panel	×						
HbA1c	×						
Total Insulin		×					1
Fibrotest and APRI (or Fibroscan or Liver Biopsy)	×						
HCV RNA	✓	×	✓	 Image: A second s	✓	×	×
HCV resistance sample		×	×	 Image: A second s	×	×	 Image: A second s
Archive sample	×	×	✓	 Image: A second s	×	×	×
Drug/Alcohol Screen	×						
Flow cytometry CD4+ (only for HCV/HIV coinfected subjects)	*						

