- HCV genotype (GT) (1, 2, 3, 4, 5, or 6) and available subtype (final HCV genotype and subtype as defined in Section 9.7);
- Cirrhosis status (cirrhotic, non-cirrhotic, or unknown test results indeterminate);
- Baseline Child-Pugh score (for cirrhotic subjects or subjects with cirrhosis status unknown; 5, 6, or > 6)
- Screening Child-Pugh score (for cirrhotic subjects or subjects with cirrhosis status unknown; 5, 6, or > 6)
- Baseline fibrosis stage (equivalent to Metavir F0 F1, F2, F3, or F4);
- Baseline HCV RNA level (< LLOQ or ≥ LLOQ; < 800,000 or ≥ 800,000 IU/mL; < 1,000,000 or ≥ 1,000,000 IU/mL);

- Baseline ALT (≤ ULN, > ULN to ≤ 3 × ULN, > 3 × ULN to ≤ 5 × ULN, > 5 × ULN to ≤ 10 × ULN, or > 10 × ULN);
- Baseline total bilirubin (< 34.2 or  $\ge$  34.2  $\mu$ mol/L);
- Baseline creatinine clearance (<  $60, \ge 60$  to <  $90, \text{ or } \ge 90$  mL/min);
- Baseline eGFR (< 90 or  $\geq$  90 mL/min/1.73 m^2);
- Baseline platelet count (< 100 or  $\ge$  100 × 10^9/L; < 150 or  $\ge$  150 × 10^9/L);
- Baseline serum albumin (< 35 or  $\geq$  35 g/L);
- Baseline APRI ( $\leq 1, > 1$  to  $\leq 2$ , or > 2);
- Baseline HOMA-IR (< 2 or  $\geq$  2 mU × mmol/L);
- Baseline FibroTest (< 0.75 or  $\geq$  0.75);

- Baseline FIB-4 (< 1.45,  $\ge 1.45$  to  $\le 3.25$ , or > 3.25);
- Baseline AST/ALT ratio ( $\leq 1 \text{ or } > 1$ );
- Baseline HCV/HIV co-infection status (HCV mono-infected or HCV/HIV-1 co-infected);
- History of diabetes (yes or no);
- History of prior HCV infection (yes or no);
- History (i.e., started prior to start of study treatment) of non-prescribed illicit drug use (yes, ongoing as of the end of study participation; yes, last dose after last dose of study treatment; yes, last dose during study treatment period; yes, last dose less than 6 months prior to start of study treatment; yes, last dose more than 12 months prior to start of study treatment; yes, last dose more than 12 months prior to start of study treatment; yes, last dose unknown; or no);

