## 15.0 Appendices

#### Appendix A. Protocol Deviations

Protocol deviations will be categorized as follows:

- Subject entered into the study even though they did not satisfy eligibility criteria;
- Subject developed withdrawal criteria during the study and was not withdrawn;
- Subject received the wrong treatment or incorrect dose of study treatment;
- Subject took a prohibited concomitant medication.

abbvie	Glecaprevir/Pibrentasvir
	M20-350 – Statistical Analysis Plan
	Version 4.0 – 12 August 2024

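### The albumin limit for subjects with cirrhosis in eligibility criterion 4 is written in mg/dL, so read literally that bullet excludes no cirrhotic subject

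*Protocol*

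**What the plan says.** Protocol section 5.1, criterion 4, opens with "Subject must not have any of the following abnormal laboratory results at screening", so a value below a stated limit excludes the subject. The albumin bullet reads "Albumin < 2.8 mg/dL for subjects with cirrhosis, < lower limit of normal for subjects without cirrhosis". Two bullets later, in the same list, hemoglobin is given as "Hemoglobin < 10 g/dL".

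The SAP handles albumin in g/L:

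- Section 7.1 divides baseline albumin at 35 g/L (the line beginning "Baseline serum albumin (< 35 or"), and section 9.6 uses the same cut for the SVR12 subgroups.
- Appendix B, Table B-1, grades albumin with boundaries at 30 and 20 g/L. Its highest albumin grade, Grade 3, is below 20 g/L.

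SAP Appendix A has a deviation category for "Subject entered into the study even though they did not satisfy eligibility criteria".

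**The concern.** The limit for cirrhotic subjects lies about three orders of magnitude below any albumin value that the SAP uses. Read as written, it cannot exclude anyone, whereas subjects without cirrhosis are held to the lower limit of normal. The group for which the protocol sets a separate albumin limit is left without a working one.

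Two things are at stake:

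- **Consistent eligibility.** A site that follows the text excludes no cirrhotic subject on albumin. A site that corrects the unit for itself applies a limit that is not written down. Sites could therefore differ, under a protocol that does not allow prospective deviations except to remove an immediate hazard (section 5.9).
- **The deviation summary.** A cirrhotic subject with low albumin who met every other criterion would not count as an eligibility deviation under the literal text, but might under a corrected reading.

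**Working it through.** **Inputs**

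- Written limit for subjects with cirrhosis: 2.8 mg/dL (Protocol 5.1, criterion 4).
- SAP albumin values: 35 g/L (7.1 and 9.6); 30 and 20 g/L (Table B-1).
- Planned enrolment: 283 (Protocol 7.8).
- Proportion with cirrhosis: not given in the documents. We assume 1% to 5%.

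**Step 1: convert the limit**

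2.8 mg/dL ÷ 1,000 mg/g = 0.0028 g/dL

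0.0028 g/dL × 10 dL/L = 0.028 g/L

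**Step 2: compare it with the SAP scale**

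| SAP value | In mg/dL (× 100) | Ratio to the written limit |
|---|---|---|
| 35 g/L (baseline and subgroup cut) | 3,500 | 35 / 0.028 = 1,250 |
| 30 g/L (upper bound of Grade 2) | 3,000 | 30 / 0.028 = 1,071 |
| 20 g/L (upper bound of Grade 3) | 2,000 | 20 / 0.028 = 714 |

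A subject in Grade 3, the worst albumin grade in the SAP, still passes the bullet unless albumin is below 0.028 g/L. In practice the number of cirrhotic subjects excluded by this bullet as written is zero.

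**Step 3: look for a correction elsewhere**

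The synopsis lists key eligibility criteria but does not restate the albumin limit. Protocol Appendix E, the summary of changes, does not mention it. The retest provision under criterion 4 covers only hemoglobin and creatinine clearance. Nothing in the text available to us corrects or explains the unit.

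**Step 4: how many subjects the bullet could concern**

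- 1% of 283 = 2.8
- 2% of 283 = 5.7
- 5% of 283 = 14.2

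On this assumption the bullet applies to about 3 to 14 subjects. Only those with low albumin who also pass every other criterion could be affected. That number is unknown and may be zero.

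**Step 5: effect on inference**

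The sample size, efficacy thresholds and confidence-interval rule in Protocol 7.8 and SAP 2.5 do not use the albumin limit, so none of them changes.

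**The case against.** The strongest reply is that this is an editorial slip with little consequence. The unit is so implausible that a site or programmer would be expected to notice it, and nothing in the documents suggests that anyone applied it literally.

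Other controls also remain. Criterion 11 says "Subject must be documented as either having no cirrhosis or as having compensated cirrhosis". Criterion 13 excludes past decompensation, criterion 16 lets the investigator exclude a subject on the laboratory profile, and criterion 4 keeps its INR and platelet limits. Criteria 7 and 17 exclude evidence that the current infection is chronic and other causes of liver disease, which should reduce the number of cirrhotic subjects further. The activity schedule in Appendix D requires a "Child-Pugh score (cirrhotic subjects and subjects with indeterminate cirrhosis status only" at Screening and Baseline, together with a hepatic decompensation assessment. A subject who failed any of these criteria would still be caught by the Appendix A deviation category.

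Most of this stands, and it is why we rate the practical effect as small. It does not supply the missing limit:

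- Criterion 16 rests on investigator opinion.
- Criterion 11 calls for Child-Pugh only when liver tests are indeterminate ("subject must demonstrate absence of decompensated cirrhosis by evaluating Child-Pugh score"), and section 5.1 sets no numeric Child-Pugh ceiling.
- Criterion 4 therefore holds the only numeric albumin limit for cirrhotic subjects in the text we have.

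Two further objections are fair. The hemoglobin unit is weak evidence, because different analytes may properly carry different units; the case rests on the SAP's own albumin scale. The Operations Manual (Protocol Appendix F) was not available to us, so we cannot say whether it states an albumin unit.

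**Conclusion.** The concern holds. The albumin limit for cirrhotic subjects is written as 0.028 g/L, between 714 and 1,250 times below the albumin values in the SAP, and it excludes no one as it stands. The finding is confined to that part of one bullet, read literally; the limit for subjects without cirrhosis works.

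The likely consequence is limited to a few eligibility decisions and to how they are counted as deviations. The figure of 3 to 14 subjects rests wholly on the assumed 1% to 5% prevalence of cirrhosis and is an upper bound within that range. The documents do not show how the screening or deviation checks were programmed, so whether any subject was affected cannot be determined from them. Because this is an operative numeric limit, it should be corrected even though efficacy inference is untouched.

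**What to change.** The sponsor should reconcile the value and unit in criterion 4 with the albumin scale in the SAP and state the intended limit. Which limit that is remains a clinical decision for the sponsor. The sponsor should then check that the screening checks, and the logic behind the SAP Appendix A eligibility-deviation category, use that same limit and unit. If enrolment is complete, the limit actually applied should still be confirmed, so that the deviation summary can be interpreted.

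The cost is a one-line protocol correction and a short check of the screening and deviation programming. No analysis, threshold or sample-size calculation needs to change.

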5.2 Contraception Recommendations

Contraception Requirements for Females

Subjects must follow the following contraceptive guidelines as specified:

• Females, of Non-Childbearing Potential

Females do not need to use birth control during or following study drug treatment if considered of non-childbearing potential due to meeting any of the following criteria:

1. Premenopausal female with permanent sterility or permanent infertility due to one of the following:

- Permanent sterility due to a hysterectomy, bilateral salpingectomy, bilateral oophorectomy
- Non-surgical permanent infertility due to Mullerian agenesis, androgen insensitivity, or gonadal dysgenesis; investigator discretion should be applied to determining study entry for these individuals.
- Postmenopausal female
 - Age > 55 years with no menses for 12 or more months without an alternative medical cause.
 - Age ≤ 55 years with no menses for 12 or more months without an alternative medical cause AND a follicle-stimulating hormone (FSH) level > 30 international units (IU)/L.
- Premenarchal female (has not met the definition of childbearing potential below)
 - Females who have not experienced menarche (at least 1 menstrual period).
- Females, of Childbearing Potential

Females who have experienced menarche (at least 1 menstrual period) prior to or during the study.

- Females of childbearing potential must avoid pregnancy while taking study drug(s) and for at least 30 days after the last dose of study drug.
- Females must commit to one of the following methods of birth control:
 - Progestogen-only hormonal birth control (oral, injectable, implantable) associated with inhibition of ovulation initiated at least 30 days prior to study Baseline Day 1.
 - Bilateral tubal occlusion/ligation (can be via hysteroscopy, provided a hysterosalpingogram confirms success of the procedure).
 - Intrauterine device.
 - Intrauterine hormone-releasing system.
 - Male or female condom with or without spermicide.
 - Cap, diaphragm, or sponge with spermicide.
 - A combination of male condom with either cap, diaphragm, or sponge with spermicide (double barrier method).
 - Vasectomized partner (provided the partner has received medical confirmation of the surgical success of the vasectomy and is the sole sexual partner of the trial subject).
 - Practice true abstinence, defined as: Refraining from heterosexual intercourse when this is in line with the preferred and usual lifestyle of the subject (periodic abstinence [e.g., calendar, ovulation, symptothermal, post-ovulation methods] and withdrawal are not acceptable).

Contraception recommendations related to use of concomitant therapies prescribed should be based on the local label.

Contraception Requirements for Males

No contraception is required for male subjects.

5.3 Prohibited Medications and Therapy

Subject must be able to safely discontinue any prohibited medications or supplements listed in Section 5.1 at least 14 days or 10 half-lives (whichever is longer) prior to the first dose of GLE/PIB and not use these during the entire Treatment Period and for 14 days following discontinuation of study drug. Subject must be consented for the study prior to discontinuing any prohibited medications for the purpose of meeting study eligibility.

In addition to the medications listed in the eligibility criteria, concomitant use of the following is NOT allowed:

- Any herbal supplements (including milk thistle), red yeast rice (monacolin K), St. John's Wort;
- Carbamazepine, phenytoin, pentobarbital, phenobarbital, primidone, rifabutin, rifampin;
- Atorvastatin, lovastatin, simvastatin;*
- Astemizole, cisapride, terfenadine;
- Atazanavir, efavirenz, oxcarbazepine, pitavastatin.

*Some HMG-CoA reductase inhibitors (including atorvastatin, lovastatin, or simvastatin) should not be taken with the study drug. Subjects receiving these statins should either switch to pravastatin or rosuvastatin 14 days or 10 half-lives (whichever is longer) prior to the first dose of study drug or may interrupt statin therapy throughout the treatment period beginning at least 14 days or 10 half-lives (whichever is longer) prior to the first dose of study drug or may interrupt statin therapy throughout the treatment period beginning at least 14 days or 10 half-lives (whichever is longer) prior to the first dose of study drug and until 14 days after the last dose of study drug, based on investigator's judgment. If switching to or continuing pravastatin or rosuvastatin, it is recommended to reduce the pravastatin dose by 50% or limit the rosuvastatin dose to 10 mg QD when taking with the study drug.

